2.3 Study Endpoints

Phase 2 Part of the Study:

Primary Endpoints for Phase 2:

- *[In the US:]* Assessment of MACrO₂ PRO instrument psychometric properties (eg, reliability, validity, ability to detect change [responsiveness], and clinically meaningful within-patient changes in scores), including assessment of symptom-based clinical response between baseline and Month 3, and baseline and Month 6, defined as improvement of ≥ 1 grade in the key symptom with no worsening of other symptoms, in the Microbiological Intent-to-Treat (Micro-ITT) Population
- *[Outside the US:]* By-subject sputum culture conversion monthly through Month 6 in the Micro-ITT Population. Sputum culture conversion will be assessed using culture conversion based on 3 consecutive monthly negative sputum cultures for MAC
- Assessment of treatment-emergent adverse events (TEAEs) and changes from baseline in clinical laboratory values, electrocardiograms (ECGs), and vital sign changes in the Safety Population

Secondary Endpoints for Phase 2:

- *[In the US:]* By-subject sputum culture conversion monthly through Month 6 in the Micro-ITT Population. Sputum culture conversion will be assessed using culture conversion based on 3 consecutive monthly negative sputum cultures for MAC
- *[Outside the US:]* Assessment of MACrO₂ PRO instrument psychometric properties (eg, reliability, validity, ability to detect change [responsiveness], and clinically meaningful within-patient changes in scores), including assessment of symptom-based clinical response between baseline and Month 3, and baseline and Month 6, defined as improvement of ≥ 1 grade in the key symptom with no worsening of other symptoms, in the Micro-ITT Population
- By-subject microbiological improvement at Month 3 and Month 6 in the Micro-ITT Population. Microbiological improvement will be assessed using decrease in MAC colony counts of ≥ 1 category
- PRO symptom/function-based clinical response using mean changes in PRO domain scores (eg, QOL-B, NTM Symptoms Module, SGRQ-C), or improvement of ≥ 1 grade in the key symptom with no worsening of other symptoms in the MACrO₂ PRO, monthly through Month 6, in the Micro-ITT and Per-Protocol (PP) populations
- Concordance analysis of PRO symptom/function-based clinical response and microbiological response (by-patient sputum culture conversion and by-patient microbiological improvement) in the Micro-ITT Population
- Rates of reinfection (new pulmonary MAC infection caused by pathogen[s] different from the baseline MAC isolate) and relapse (pulmonary MAC infection caused by the same baseline MAC isolate) at Month 6, EOT, and LFU in the Micro-ITT Population
- Characterization of epetraborole plasma exposure in the population PK model

Exploratory Endpoints for Phase 2:

- Clinical response and microbiological response (by-subject sputum culture conversion and by-subject microbiological improvement) at Month 3 and Month 6 presented by age category, presence/absence of any fibrocavitary disease, ALIS use at baseline, and MAC resistance phenotype (ie, macrolide-resistant and amikacin-resistant) in the Micro-ITT Population
- Radiographic response at Month 6 and EOT, defined as overall change from baseline based on blinded central reading of chest computed tomography (CT) in the Micro-ITT Population
- By-subject microbiological response (by-subject sputum culture conversion and by-subject microbiological improvement) by epetraborole MIC at Month 6 in the Micro-ITT Population
- Rate of decreased susceptibility among postbaseline MAC isolates, defined as a ≥ 4 -fold increase in epetraborole MIC relative to the baseline isolate MIC, among patients remaining MAC culture-positive at Month 4 or later in the Micro-ITT Population
- Time (in days) to improvement in PRO-based clinical response in the Micro-ITT Population
- Time (in months) to first negative sputum culture and decrease in MAC colony counts by ≥ 1 category in the Micro-ITT Population
- Qualitative assessment of the appropriateness of the proposed symptom-based clinical response definition that uses the MACrO₂ PRO in the Micro-ITT Population.

Phase 3 Part of the Study:

Primary Endpoint for Phase 3:

- *[In the US:]* Pending verification from the Phase 2 part of the study: MACrO₂ PRO symptom-based clinical response, defined as improvement of ≥ 1 grade in the key symptom with no worsening of other symptoms between baseline and Month 6 in the Micro-ITT Population

- *[Outside the US:]* By-subject sputum conversion based on 3 consecutive monthly negative sputum cultures for MAC by Month 6 in the Micro-ITT Population

Secondary Endpoints for Phase 3:

- *[In the US:]* Key secondary endpoint: By-subject sputum conversion based on 3 consecutive monthly negative sputum cultures for MAC by Month 6 in the Micro-ITT Population
- *[Outside the US:]* Key secondary endpoint: Pending verification from the Phase 2 part of the study: MACrO₂ PRO symptom-based clinical response, defined as improvement of ≥ 1 grade in the key symptom with no worsening of other symptoms between baseline and Month 6 in the Micro-ITT Population
- By-subject microbiological improvement at Month 3 and Month 6 using decrease in MAC colony counts of ≥ 1 category in the Micro-ITT Populations
- PRO symptom/function-based clinical response using mean changes in PRO domain scores (eg, QOL-B, NTM Symptoms Module, SGRQ-C), or improvement of ≥ 1 grade in the key symptom with no worsening of other symptoms in the MACrO₂ PRO, monthly through Month 6, in the Micro-ITT and Per-Protocol populations
- Concordance analysis of PRO symptom/function-based clinical response and microbiological response (by-subject sputum culture conversion and by-subject microbiological improvement) in the Micro-ITT Population
- Rates of reinfection (new pulmonary MAC infection caused by strain[s] different from the baseline MAC isolate) and relapse (pulmonary MAC infection caused by the same baseline MAC isolate) at Month 6, EOT, and LFU in the Micro-ITT Population
- Assessment of TEAEs and changes from baseline in clinical laboratory values, ECGs, and vital sign changes in the Safety Population
- Characterization of epetaborole plasma PK in the PK Population

Exploratory Endpoints for Phase 3:

- Clinical response and microbiological response (by-subject sputum culture conversion and by-subject microbiological improvement) at Month 3 and Month 6 presented by age category, presence/absence of any fibrocavitary disease, ALIS use at baseline, and MAC resistance phenotype (macrolide-resistant and amikacin-resistant) in the Micro-ITT Population
- Radiographic response at Month 6 and EOT, defined as overall change from baseline based on blinded central reading of chest CT in the Micro-ITT Population
- By-subject microbiological response (by-subject sputum culture conversion and by-subject microbiological improvement) by epetaborole MIC at Month 6 in the Micro-ITT Population
- Rate of decreased susceptibility among postbaseline MAC isolates, defined as a ≥ 4 -fold increase in epetaborole MIC relative to the baseline isolate MIC, among patients remaining MAC culture-positive at Month 4 or later in the Micro-ITT Population
- Time (in days) to improvement in PRO-based clinical response in the Micro-ITT Population
- Time (in months) to first negative sputum culture and decrease in MAC colony counts by ≥ 1 category in the Micro-ITT Population

3 STATISTICAL METHODOLOGY

3.1 General Considerations

3.1.1 Analysis Day

Study days are calendar days, rather than 24-hour days. Analysis day will be calculated from the date of first dose of study drug. The day of the first dose of study drug will be Day 1, and the day immediately before Day 1 will be Day -1. There will be no Day 0. Any durations in days will be derived as event stop date – event start date + 1.

3.1.2 Definition of Baseline

For PRO data entered by the patient (MACrO₂, QOL-B, NTM Symptoms Module, SGRQ-C, or PGIS), baseline is defined as the last entry recorded by the patient on or prior to the first dose of study drug + 1 day (ePRO-specified close of window to further entry to patients).

For PRO data entered by the site (CGIS), baseline is defined as the last entry recorded by the patient on or prior to the first dose of study drug + 6 days (ePRO-specified close of window to further entry to sites).

For microbiological data, baseline pathogen(s) are determined based on MAC pathogens isolated from all MAC-positive respiratory samples collected within the 8-week Screening Period prior to the first dose of study drug, with specific representative baseline pathogen(s) confirmed by blinded Sponsor review.

For all other efficacy and safety endpoints, baseline is defined as the last measurement or assessment prior to first dose of study drug, including results from unscheduled visits if applicable.

3.1.3 Summary Statistics

Categorical data will generally be summarized with counts and percentages of patients. The denominator used for the percentage calculation will be clearly defined. Continuous data will generally be summarized with descriptive statistics including n (number of non-missing values), mean, median, standard deviation, minimum, and maximum. Summaries of continuous variables that have some values recorded using approximate values (e.g., “<” or “>” for safety laboratory results) will use the numeric part of the value in calculations, while listings will present the data in its original format (e.g., “<X.X”).

3.1.4 Handling of Dropouts and Missing Data

Every effort will be made to collect all data at specified times. Missing data will be handled as outlined below:

- All missing and partial dates for AEs after randomization will be queried for a value. If no value can be obtained, substitutions will be made as follows:
For a missing start day where the month and year are present, the start day will be set to the first day of the month, unless 1) the first day of the month is before the date of administration of study drug and the month and year are the same as the month and year of the date of administration of study drug, and 2) the end date is on or after the date of administration of study drug or the end date is completely missing, in which case the start day will be set to the day of administration of study drug.
For a missing start day and month where the year is present, the start day and month will be set to January 1st, unless 1) January 1st is before the date of administration of study drug and the year is the same as the year of the date of administration of study drug, and 2) the end date is on or after the date of administration of study drug or the end date is completely missing, in which case the start day and month will be set to that of the date of administration of study drug.

For a missing end day where the month and year are present, the end day will be set to the last day of the month, unless the month and year are the same as the month and year of the last contact date for the patient, in which case the end day will be set to that of the patient's last contact date.

For a missing end day and month where the year is present, the end day and month will be set to the patient's last contact date, unless the year of the patient's last contact date is greater than the end year, in which case the end day and month will be set to December 31st.

These substitutions will be used in analyses; however, the actual partial or missing date recorded on the eCRF will be presented in listings.

- Missing dates for prior and concomitant medications will be queried for a value. If no value can be obtained, missing data will be handled as follows:

For a missing start date, 1) if only the day component is missing, the start day will be set to the first day of the month, and 2) if both day and month components are missing, the start day will be set to January 1st.

For a missing end date, 1) if only the day component is missing, the end day will be set to the last day of the month, and 2) if both day and month components are missing, the end date will be set to December 31st.

- If no value can be obtained for times for events and assessments occurring after randomization, the time will not be imputed but will remain missing.
- Severity and causality assessments for adverse events cannot be missing. Missing data will be queried for a value.

For clinical and microbiological responses, missing data will be handled as follows:

- Missing symptom data from MACrO₂ PRO responses:
 - All MACrO₂ PRO responses with missing entries will trigger alerts and will be followed up for a complete response. However, if any remain only partially completed, the patient will be considered to have missing data if an assessment of any of their seven MAC lung disease symptom(s) are not made in the MACrO₂ PRO at the protocol-defined time points of Month 3 and Month 6. Patients with any missing or incomplete Month 3 or Month 6 MACrO₂ PRO symptom data will be defined as an indeterminate response at the corresponding time point (Month 3 or Month 6), and will be considered clinical non-responders for PRO symptom-based clinical response analyses in the Micro-ITT Population in both the Phase 2 and Phase 3 parts of the study. For model-based (MMRM) analyses of MACrO₂ PRO response over time, patients with one or more missing visits will be retained in the model, with no imputation methods applied to those missing results.
- Missing data from other PRO responses (QOL-B, NTM Symptoms Module, SGRQ-C, and the MACrO₂ total scaled score analyzed in Phase 3):
 - If individual items within the PRO score are missing, the approved algorithm (See Appendix) for calculating the domain score or total score will scale the response to account for the missing items. However, if the number of missing items is more than the allowance of the algorithm to enable the scaling to be reliably performed, the score will be considered missing for that visit, and handled as an entirely missing visit as per the bullet above.
 - For analyses of domain scores or total scores, a longitudinal analysis will be performed which will include data recorded at all time points up to Month 6 and will provide estimates of treatment effect at the relevant time points (Months 3 and 6). Missing data is not expected, but if there is a larger than expected amount of missing data, further analyses to assess the impact of missing data may be undertaken using missing data imputation methods.

- For analyses of QOL-B response, NTM Symptoms Module response, and SGRQ-C response, a patient will be considered to have missing data if the relevant score is not completed at the protocol-defined time points of Month 3 and Month 6. Patients with missing Month 3 or Month 6 data will be defined as an indeterminate response at the corresponding time point (Month 3 or Month 6), and will be considered clinical non-responders. For model-based analyses of PRO measures over time, patients with one or more missing visits will be retained in the model, with no imputation methods applied to those missing results.
- Missing microbiological culture data:
 - For patients with no available sputum for culture despite attempted sputum collection — and if the patient was previously sputum culture negative for MAC at their last post-baseline available monthly assessment — the microbiological outcome will be assessed as culture negative for that visit and the MAC colony count category will be assessed as “No growth on agar or broth” at that visit. All other patients with missing sputum culture results that impacted the ability to assess sputum culture conversion (i.e., 3 consecutive months of negative sputum cultures) or categorical decreases in MAC colony counts will be considered microbiological non-responders.
- Missing colony count data:
 - As it is not uncommon for MAC pathogens to grow on liquid culture media (broth) but not on agar media, it is anticipated that there will be some sputum samples for which colony count cannot be obtained. For each sputum specimen in which growth of a MAC pathogen is identified in broth but colony counts on agar are not available, such results will be assessed as missing. In cases where a baseline colony count is not available, such patients will be excluded from the denominator for all analyses of microbiological improvement. In cases of post-baseline visits where a MAC pathogen is grown in broth but a colony count is not available, such patients will be categorized as “Missing” in summary statistics and considered non-responders with regard to microbiological improvement at that visit. In cases of post-baseline visits where no growth is seen in broth and a colony count is not available, such patients will be categorized as “No growth on agar or broth” and colony count of 0 at that visit.

Missing values for other individual data points will remain as missing. Missing values will not be imputed and only observed values will be used in data analyses and presentations. Where individual data points are missing, categorical data will be summarized based on reduced denominators (i.e., only patients with available data will be included in the denominators).

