7.5.3.4. Testing

Sputum samples collected during the Screening Period and at designated time points during the study will be sent to the regional or central microbiological laboratory for mycobacterial culture, identification and quantification. Susceptibility testing and molecular testing (if applicable) of isolates will be performed at the central microbiological laboratory.

The time from receipt of sputum at the regional or central microbiological laboratory to a MAC-positive culture averages 3 weeks but may take up to 6 weeks. In addition, identification of MAC isolates to the species level using the line probe assay (LPA) or matrix-assisted laser desorption ionization-time of flight (MALDI-TOF) mass spectrometry, averages 1 to 3 days. Isolates that cannot be identified or speciated using LPA or MALDI-TOF will be identified and speciated via sequencing of the *rpoB* gene or 16S rRNA, which takes up to an additional 7 days.

Microbiological evaluation of sputum samples will include improvement in quantitative colony counts. Quantification of bacteria via colony counts on solid agar will be performed and assigned a categorical score similar to that reported by Griffith, et al. where colony counts were predictive of symptomatic and radiographic improvement ([Griffith, 2015](#)) (see [Table 1](#)). An improvement in quantitative culture counts will be defined as a reduction in ≥ 1 categorical score from the screening isolate and the previous month's categorical culture score.

Table 1: Categorical Scoring for Quantitative Culture Counts

Colonies (CFU/mL)	Categorical Culture Score ^a
No growth on agar or broth	0
Growth in broth only	1
1-49	2
50-99	3
100-199	4
200-299	5
≥300	6

Abbreviation: CFU = colony-forming units.

^a Categorical scores based on those reported in [Griffith, 2015](#).

The regional and/or central microbiological laboratory will follow standardized methods and procedures for MAC culture, identification, and susceptibility testing (following CLSI guidelines). All respiratory culture specimens will be cultured in appropriate liquid and solid media. If the results are negative on solid media, the liquid media will be held for 6 weeks before reporting the culture as negative.

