3.4.1.3 Phase 2 Secondary Efficacy Endpoints at Month 6 Analysis

The secondary efficacy endpoints include microbiological response (by-patient sputum culture conversion and by-patient microbiological improvement) monthly through Month 6, PRO symptom-based clinical response (mean changes in PRO domain scores or improvement of ≥1 grade in the key symptom with no worsening of other symptoms in the MACrO₂ PRO) monthly through Month 6, concordance of clinical response and microbiological response (concordance between PRO response and microbiological response), and rates of recurrence, reinfection, and relapse by Month 6.

“Microbiological response” is defined as sputum culture conversion based on 3 consecutive monthly negative sputum cultures for MAC by Month 6; “microbiological improvement” is defined as a decrease in MAC colony counts of ≥ 1 category from baseline. By-patient microbiological response by Month 6 and by-patient microbiological improvement at Month 3 and Month 6 (see details below) will be presented for the Micro-ITT Population. Descriptive statistics (n, %) will be presented by visit and treatment group. Treatment difference, associated 95% confidence interval and p-value at Month 3 and Month 6, will be calculated using the method of Miettinen and Nurminen, both including (primary analysis) and excluding (sensitivity analysis) stratification by baseline ALIS use and age (<65 years versus ≥ 65 years).

By-patient microbiological improvement (decrease in MAC colony counts of ≥ 1 category from baseline) will be summarized using the categories of 0 = no growth on agar or broth; 1 = growth in broth only; 2 = 1 to 49 CFU/mL; 3 = 50 to 99 CFU/mL; 4 = 100 to 199 CFU/mL; 5 = 200 to 299 CFU/mL; 6 = ≥ 300 CFU/mL, where specific colony counts are based on solid agar growth. If more than one sputum sample at the same visit is culture positive for the same species of MAC, the culture with the highest colony count will be used for determination of microbiological improvement.

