The secondary efficacy endpoints include microbiological response (by-patient sputum culture conversion monthly through Month 6 and by-patient microbiological improvement at Month 3 and Month 6), PRO symptom-based clinical response (mean changes in PRO domain scores or improvement of ≥ 1 grade in the key symptom with no worsening of other symptoms in the MACrO₂ PRO) monthly through Month 6, concordance of clinical response and microbiological response (concordance between PRO response and microbiological response), and rates of recurrence, reinfection, and relapse by Month 6.

“Microbiological response” is defined as sputum culture conversion based on 3 consecutive monthly negative sputum cultures for MAC by Month 6; “microbiological improvement” is defined as a decrease in MAC colony counts of ≥ 1 category from baseline. By-patient microbiological response at Months 6 and by-patient microbiological improvement by Month 3 and Month 6 will be presented for the Micro-ITT Population. Descriptive statistics (n, %) will be presented by visit and treatment group. Treatment difference, associated 95% confidence interval and p-value at Month 3 and 6, will be calculated using the method of Miettinen and Nurminen, both including (primary analysis) and excluding (sensitivity analysis) stratification by baseline use of ALIS and the presence or absence of any fibrocavitary disease.

By-patient microbiological improvement (decrease in MAC colony counts of ≥ 1 category from baseline) will be summarized using the categories of 0 = no growth on agar or broth; 1 = growth in broth only; 2 = 1 to 49 CFU/mL; 3 = 50 to 99 CFU/mL; 4 = 100 to 199 CFU/mL; 5 = 200 to 299 CFU/mL; 6 = ≥ 300 CFU/mL. If more than one sputum sample at the same visit is culture positive for the same species of MAC, the culture with the highest colony count will be used for determination of microbiological improvement.

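### SAP 3.1.4 sets growth in broth without an agar count to missing, while the endpoint's own 0–6 scale scores broth-only growth as category 1

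*SAP*

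**What the plan says.** Protocol 7.5.3.4, Table 1, gives a seven-level score from 0 to 6 in which "Growth in broth only" is category 1. SAP 3.4.3.3 repeats it for Phase 3: "0 = no growth on agar or broth; 1 = growth in broth only; 2 = 1 to 49 CFU/mL", and so on up to 6. SAP 3.4.1.3 has the same level for Phase 2 ("1 = growth in broth only"). In SAP 3.4.3.3, microbiological improvement "is defined as a decrease in MAC colony counts of ≥ 1 category from baseline".

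SAP 3.1.4, under missing colony count data, begins by observing that "it is not uncommon for MAC pathogens to grow on liquid culture media (broth) but not on agar media", and therefore expects some samples to have no count. It then rules on specimens with MAC growth "identified in broth but colony counts on agar are not available, such results will be assessed as missing". There are two consequences:
- With no baseline count, "such patients will be excluded from the denominator for all analyses of microbiological improvement".
- With broth growth and no count after baseline, patients are labelled Missing and "considered non-responders with regard to microbiological improvement at that visit".

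If broth shows no growth and there is no agar count, the same paragraph assigns category 0.

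**The concern.** One laboratory result, agar negative and broth positive, gets two scores. The scale treats it as an observed low burden of organisms. The missing-data rule treats it as no information and then imputes failure.

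It is a completed result. Protocol 7.5.3.4 has every specimen cultured in both liquid and solid media, and the liquid culture is held for six weeks when the solid one is negative. The rule is also uneven: without an agar count, negative broth is enough for category 0, but positive broth is not enough for category 1. SAP 3.1.4 further allows a visit with no obtainable sputum, after a previous negative culture, to be scored category 0. So an absent sample can count as improvement while an observed low-level culture counts as failure.

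Microbiological improvement at Months 3 and 6 is a named Phase 3 secondary endpoint, reported with a confidence interval and p-value. It also enters the tables of PRO response against improvement. The colony-count category itself enters further concordance tables and the PRO scatterplots. In Phase 2 it underlies the improvement table and the time to first sustained decrease.

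**Working it through.** The plan states no rate, power or sample size for microbiological improvement, so there is no figure to reproduce. SAP 2.2.7 covers clinical response and culture conversion only.

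**Step 1: score every transition both ways.** Baseline categories 1–6 by post-baseline categories 0–6 give 6 × 7 = 42 transitions. By the scale, a patient responds if baseline minus post-baseline is at least 1. By SAP 3.1.4 as written, baseline category 1 is excluded and post-baseline category 1 is a non-response.

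| Transition | By the scale | By SAP 3.1.4 |
|---|---|---|
| 6→5 | responder | responder |
| 6→1, 5→1, 4→1, 3→1, 2→1 | responder | Missing, non-responder |
| 1→0 | responder | excluded |
| 1→1 to 1→6 | non-responder | excluded |

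The scale has 1+2+3+4+5+6 = 21 responder transitions and SAP 3.1.4 has 15. The six lost are the five falls to category 1 and the clearance 1→0.

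**Step 2: effect on one arm's rate.** Define four shares:
- b: patients broth-only at baseline
- r: improvement rate under SAP 3.1.4 among the rest
- f: share of the rest who fall to broth-only
- c: share of baseline broth-only patients who clear to 0

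Rate under SAP 3.1.4 = r. Rate under the scale = (1−b)(r+f) + b·c. Change = (1−b)·f − b·(r−c).

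Assumed example with 100 patients: 20 are broth-only at baseline, of whom 5 clear and 15 stay. Of the other 80, 24 improve with a usable count and 5 fall to broth-only.
- SAP 3.1.4: 24/80 = 30%.
- Scale: (24+5+5)/100 = 34%, a change of 4 points. By the formula, 0.8 × 0.0625 − 0.2 × (0.30−0.25) = 0.05 − 0.01 = 0.04.
- If none of the 80 fall to broth-only and none of the 20 clear, the scale gives 24/100 = 24%, which is 6 points lower.

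**Step 3: effect on the treatment difference.** Assume no broth-only patients at baseline and other improvement of 30% on epetraborole and 20% on placebo. The difference under SAP 3.1.4 is then always 10 points.

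| Falls to broth-only (epetraborole, placebo) | Rates by the scale | Difference by the scale |
|---|---|---|
| 5%, 5% | 35%, 25% | 10 points |
| 10%, 5% | 40%, 25% | 15 points |
| 20%, 10% | 50%, 30% | 20 points |
| 5%, 10% | 35%, 30% | 5 points |

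All rates in Steps 2 and 3 are assumptions; the documents give none.

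**Step 4: which visits are affected.** Two to three samples are collected at each visit, and SAP 3.4.3.3 uses the culture with the highest count. A visit is affected only if none of its samples has an agar count.

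**The case against.** The best defence is a narrower reading: an agar count that is not available could mean a plate that was lost, contaminated or not read. Category 1 would then remain usable for agar read as no growth. This fits the SAP's retention of category 1 in both phases, and the concordance tables in 3.4.1.3 and 3.4.3.3, which list Missing and 1 as separate levels. It does not fit the rule's own opening sentence, which gives growth in broth but not on agar as the reason a count cannot be obtained. No sentence separates the two situations, so even on this reading two programmers could derive different results from the same data. What stands is that the SAP may have intended the distinction, so one cannot say that category 1 is unusable on every reading.

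Three stronger inferences are tempting, and the documents support none of them:
- **The rule hides benefit on epetraborole.** No broth-only rates by arm are given, and Step 3 shows the difference moving either way. SAP section 1 reports that epetraborole was not superior on culture conversion in Phase 2, so a larger microbiological shift on active drug cannot be presumed.
- **The understatement equals the share of patients broth-only at Month 6.** Only falls from a countable baseline become responses, and restored baseline broth-only patients enlarge the denominator. In the first Step 2 example, 20 of 100 patients are broth-only at Month 6 and the rate changes by 4 points.
- **The trial's main conclusions are at risk.** Improvement is not among the three Phase 3 endpoints in the hierarchy of SAP 3.4, which intends no claims from other secondary endpoints. Conversion is unaffected because broth growth is a positive culture under either rule.

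**Conclusion.** The concern holds as a conflict between SAP 3.1.4 and the scale in Protocol Table 1 and SAP 3.4.1.3 and 3.4.3.3. On the text as written, six of the scale's 21 responder transitions do not count as responses: five are scored as failures and one is excluded. A one-category fall from 6 to 5 succeeds where a five-category fall from 6 to 1 fails.

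The reach is limited to microbiological improvement, the concordance tables and the scatterplots, together with the Phase 2 analyses built on the same definition. The effect on the treatment difference is indeterminate in size and direction. If falls to broth-only growth are equally frequent in both arms, the difference is roughly unchanged. This verdict rests on taking the opening sentence of the rule as defining its scope. If the narrower reading was intended, the defect is one of missing clarity, and the same amendment cures it.

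**What to change.** Before Phase 3 unblinding, amend SAP 3.1.4 as follows:
- Agar read as no growth with broth positive for MAC is category 1, at baseline and at every post-baseline visit, in both numerator and denominator.
- Missing is reserved for specimens with no usable agar result: not set up, contaminated or unreadable.

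Apply this to the Phase 3 improvement, concordance and scatterplot outputs. Any rerun of the Phase 2 improvement table should be labelled post hoc in the CSR. SAP section 1 limits later SAP changes to Phase 3, and section 3.4 treats the Phase 2 Month 6 efficacy results as final and not to be repeated.

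The cost is a short text change and one derivation. Both culture media are already required, so no new assessment is needed. The data manager should confirm that the laboratory data separate agar read as no growth from agar with no result, which the protocol and SAP do not show. After unblinding, the same change would be a documented deviation and could look driven by the results.
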